4.2 Prescreening and Screening Log

The MCW study principal investigator regularly reviews screen failure reasons to understand barriers to accrual and consider amending eligibility criteria. Screen failures are defined as participants who were considered for the trial to participate in the clinical trial with or without consent but are not subsequently assigned to the study intervention or enrolled in the study.

MCW Protocol No: PRO00035737 27 Version No. 7 MCWCC CTO will follow its SOPs regarding prescreening and screening tracking.

4.3 Consent

Investigators or their appropriate designees will identify potentially eligible subjects from their clinics, subject self-referrals, referrals from other clinicians and/or other IRB-approved recruitment methods. No study conduct, including subject prescreening, can occur until after IRB approval.

A written, signed informed consent form (ICF) must be obtained before any study-specific assessments are initiated. A signed ICF copy will be given to the subject and a copy will be filed in the medical record (per local IRB policies and SOPs). The original will be kept on file with the study records.

4.4 Screening Procedures

Refer to study calendar of events.

Visit procedures that were performed as standard of care prior to consent (without the specific intent to make the subject eligible for the trial), may count towards screening tests and eligibility if they are within the screening window.

MCW Protocol No: PRO00035737 Version No. 7 28

Subject Initials:	Subject Study ID:	Enrolling Physician
4.5 Eligibility Confirmation	ion	
Study staff must adhere to	MCWCC CTO SOPs rega	ding eligibility review/confirmation.
meet all inclusion and excluding all study aspects, including requirements for informed	usion criteria. In addition, the g the study visit schedule a d consent. The written info t. The following criteria ap	prior to the first study drug dose and must be patient must be thoroughly informed about and required evaluations and all regulatory rmed consent must be obtained from the bly to all patients enrolled onto the study,
		g the pretransplant period but is no longer they will be removed and replaced on
item are unclear or que		when clinical factors relating to an eligibility cipal investigator ([name] ification on eligibility.
Inclusion Criteria		
acute myeloid leu complete remissio maturation of all ce disease). Patients bone marrow, no complete concentradiation [TBI] ≥5 oral or >6.4 mg/kg 4. T cell-replete perip 5. Patients must have B and -C for relat unrelated donors). 6. Cardiac function: L	kemia (AML) and acute ly in at the time of alloHCT ellular components in the bound with myelodysplastic syndrousirculating blasts. ditioning (MAC) regimen, based intravenous). So intravenous graft. So a matched related or unrested donors and at least 8/6 and clearance ≥40 mL/minus.	which alloHCT is indicated. Patients with ymphoblastic leukemia (ALL) must be in (<5% blasts in the bone marrow, normal one marrow and absence of extramedullary ome (MDS) must have <10% blasts in the sed on CIBMTR criteria (total body actionated or busulfan [Bu] dose >8 mg/kg lated donor (at least 6/6 match at HLA-A, -8 match at HLA-A, -B, -C and -DRB1 for ion ≥45% for myeloablative conditioning. the (using the Cockcroft-Gault formula and
8. Pulmonary function	n: DLCO ≥40% (adjusted fo	r hemoglobin) and FEV1 ≥50%. If normal and ALT/AST <5 x upper normal
10. Female subjects m Postmenopausal fo	nust meet one of the followir or at least one year before e sterile (i.e., undergone a hys	
CRC Initials:		Date:

MCW Protocol No: PRO00035737 29 Version No. 7

Investigator/Enrolling Physician Initials:_____

Subject Initials:	Subject Study ID:	Enrolling Physician

- b. If subject is of childbearing potential (defined as not satisfying either of the above two criteria), she must agree to practice two acceptable methods of contraception (combination methods require use of two of the following: diaphragm with spermicide, cervical cap with spermicide, contraceptive sponge, male or female condom, hormonal contraceptive) from the time of signing of the informed consent form through 90 days after the last dose of study agent, **OR**
- c. Agrees to practice true abstinence when this is in line with the preferred and usual lifestyle of the subject. (Periodic abstinence [e.g., calendar, ovulation, symptothermal, post ovulation methods] and withdrawal are not acceptable contraception methods.)
- 11. Male subjects, even if surgically sterilized (i.e., status postvasectomy), must agree to one of the following:
 - a. Practice effective barrier contraception during the entire study period and through 60 calendar days after the last dose of study agent, **OR**
 - b. Agree to practice true abstinence when this is in line with the preferred and usual lifestyle of the subject. (Periodic abstinence [e.g., calendar, ovulation, symptothermal, post ovulation methods] and withdrawal are not acceptable methods of contraception.)
- 12. Signed informed consent: Voluntary written consent must be given before patient registration and performance of any study-related procedure not part of standard medical care, with the understanding that consent may be withdrawn by the patient at any time without prejudice to future medical care.
- 13. Planned post-transplant maintenance therapy is allowed.
- 14. Prior autologous transplant is allowed.

Exclusion Criteria

- 1. Prior allogeneic HCT.
- 2. Active CNS involvement with malignancy.
- 3. Patients receiving cord blood or haploidentical allograft.
- 4. Patients undergoing in vivo or ex vivo T cell-depleted alloHCT.
- 5. Karnofsky performance score <60% or ECOG > or = 2.
- 6. Patients with uncontrolled bacterial, viral or fungal infections (currently on treatment and with progression of infectious disease or no clinical improvement) at time of enrollment.
- 7. Active hepatitis B or C virus infection or known human immunodeficiency virus (HIV) positive.
- 8. Use of rituximab, alemtuzumab, anti-thymocyte globulin (ATG), or other monoclonal antibody planned as part of conditioning regimen for GVHD prophylaxis.
- 9. Participation in another GVHD prophylaxis clinical trial.

CRC Initials:	Date:	
Investigator/Enrolling Physician Initials:	Date:	

Subject Initials:	Subject Study ID:	Enrolling Physician
arrhythmias, NY electrocardiograp abnormalities. 11. Any serious me potentially interfe	THA class III or IV congestive on the congestive of active is edical or psychiatric illness there with the completion of treating the completion of the completion of treating the completion of the comp	ditions, including uncontrolled ventricular re heart failure, uncontrolled angina, of chemia or active conduction system that could, in the investigator's opinion ment according to this protocol.
"I have reviewed all inclu	usion and exclusion criteria and	d confirm the subject is eligible."
(CRC Signat	ture)	(Date)
(Investigator/Enrolling	Physician Signature)	(Date)

4.6 Discontinuation of Study Treatment, Withdrawal, and Compliance

Discontinuation from the study treatment does not mean discontinuation from the study. Subject will be considered in follow-up, study procedures should still be completed as indicated by the study protocol and AEs/SAEs will continue to be reported according to this protocol.

In the absence of treatment delays due to adverse events, study treatment/intervention may continue until:

- Disease (relapse or progression of the primary malignancy) for which treatment is indicated.
- Donor leukocyte infusion (DLI) prior to planned redose of tildrakizumab for any indication: infection, disease control or to address mixed chimerism.
- Grade III-IV acute GVHD. Patients with grade I-II acute GVHD and on topical or systemic corticosteroids therapy (equivalent to prednisone ≤20 mg/d) can receive further doses of tildrakizumab.
- Active chronic GVHD requiring systemic therapy.
- General or specific changes in the subject's condition renders the subject unacceptable for further treatment in the investigator's judgment.
- Inter-current illness that prevents further treatment administration.
- Subject decides to withdraw from the study.
- The subject has significant noncompliance with the protocol (see below).
- Unacceptable adverse event(s) beyond requirements as detailed in this protocol.

Subjects who sign the informed consent form, and are enrolled and receive the study intervention. but subsequently withdraw, or are withdrawn or discontinued from the study will not be replaced.

Consent Withdrawal

A subject may decide to withdraw from the study at any time. MCWCC CTO will follow its IRB of record's SOPs regarding consent withdrawal.

If a subject intends on withdrawing consent, staff should confirm which of the following options the subject chooses and document the discussion:

- Full consent withdrawal, with no study follow-up.
- Selective consent withdrawal from interventional portion of the study, but agrees to continued follow-up of associated clinical outcome information.

Investigator-initiated Withdrawal

The investigator will withdraw a subject whenever continued participation is no longer in the subject's best interests. Reasons for withdrawing a subject include, but are not limited to, disease progression, the occurrence of an adverse event or a concurrent illness, a subject's request to end participation, a subject's noncompliance or simply significant uncertainty on the part of the investigator that continued participation is prudent. The reason for study withdrawal and the date the subject was removed from the study must be documented.

MCW Protocol No: PRO00035737 32 Version No. 7 Version Date: 10/31/2022

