4.1 Subject Status

Subject statuses throughout the trial are defined as follows:

- Prescreening: preconsent (subject considering trial or study staff considering patient for the trial per institutional recruitment methods).
- Screening: period after consent, but prior to eligibility confirmation.
- Consented: consented, prior to eligibility confirmation.
- Eligible: the local investigator confirms all eligibly criteria apply.
- On study/enrolled: date eligibility is confirmed.
- On arm: date of enrollment.
- On treatment: first day treatment was given to the last day treatment was given.
- Off treatment: the last day treatment was given.
- On follow-up: from last day of treatment to the end of follow-up period.
- Off study: follow-up period completed, with no additional data gathered.
- Withdrawn: subject fully withdraws consent (i.e., refuses ALL follow-up, even survival) or is taken off study by the local PI.

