6.6 Follow-up Period

Patients will be followed for a total 12 months or until death, whichever occurs first. All patients who receive at least one dose of the study drug will be followed.

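### The investigator-withdrawal clause lets dosed patients leave the study for prognostic reasons, against the rule that every dosed patient is followed; outcome data could be lost, probably in the drug's favour

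*Combined protocol and SAP*

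**What the plan says.** Two sets of rules apply to the same events.

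**Follow-up continues.** Section 4.6 opens with "Discontinuation from the study treatment does not mean discontinuation from the study". Its list of reasons to stop treatment includes relapse or progression, intercurrent illness, unacceptable adverse events and significant noncompliance. Section 6.6 says "Patients will be followed for a total 12 months or until death, whichever occurs first" and "All patients who receive at least one dose of the study drug will be followed".

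**The patient leaves the study.** The Investigator-initiated Withdrawal paragraph of 4.6 applies a best-interest test and then says: "Reasons for withdrawing a subject include, but are not limited to, disease progression, the occurrence of an adverse event or a concurrent illness". A subject's own request, noncompliance and investigator uncertainty complete the list. The paragraph ends: "The reason for study withdrawal and the date the subject was removed from the study must be documented". Section 4.1 defines the status as "Withdrawn: subject fully withdraws consent (i.e., refuses ALL follow-up, even survival) or is taken off study by the local PI", and the neighbouring status as "Off study: follow-up period completed, with no additional data gathered".

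Dosed patients who "but subsequently withdraw, or are withdrawn or discontinued from the study will not be replaced". GRFS (10.3.1) and OS (2.5, item 8) are censored at last follow-up. The analysis population is all patients with at least one dose (10.3).

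**The concern.** A site can apply either rule to the same patient. Under the first, a patient who relapses or has a severe infection is still observed for GVHD and survival. Under the second, data stop on the removal date and the patient is censored there.

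Kaplan-Meier estimation assumes that censoring is unrelated to prognosis. Progression, toxicity and intercurrent illness are all related to it. The trial has one arm and a fixed 20% reference, so no control group would share the distortion. Section 10 has no rule or sensitivity analysis for censoring at investigator withdrawal.

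**Working it through.** **1. Do the texts conflict?** Progression, adverse events, illness and noncompliance appear both as reasons to stop treatment with follow-up continuing and as reasons for removal from the study. The option to leave the intervention but keep outcome follow-up is offered only under Consent Withdrawal. The noncompliance item in the treatment list points to text below it, and the only later text on noncompliance in 4.6 is the withdrawal paragraph. So a treatment-stopping reason leads into the removal rule. The conflict is real.

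**2. Which endpoints are exposed?**

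| Withdrawn for | GRFS, PFS, relapse | OS | NRM | Acute/chronic GVHD | 100-day monitoring |
|---|---|---|---|---|---|
| Progression, already recorded | Not affected: event has occurred | Later death lost | Not affected: competing event has occurred | Later GVHD lost; 2.5 does not treat relapse as competing | Affected if before day 100 |
| Toxicity, illness or uncertainty, before any event | Censored | Censored | Censored | Censored | Affected if before day 100 |

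The last column follows from 10.5. Only patients alive with 100 days of follow-up, or with the monitored event, are evaluable. A patient withdrawn on day 60 who dies unrecorded on day 80 enters neither the count of deaths nor the denominator.

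**3. The plan's own figures.** The plan gives no rate for investigator withdrawal. The nearest figure is the 10% loss allowance in 10.2.1. The stated powers of 80%, 94% and 54% reproduce with a null-variance z-test at n = 50 (80.1%, 93.9%, 54.3%), close to 55 × 0.9 = 49.5. An allowance of that kind covers lost precision. It does not cover bias from who is lost.

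**4. GRFS (assumed rates).** Let G be the true 12-month GRFS in all dosed patients, w the proportion withdrawn early, and g the event-free probability of those withdrawn. The Kaplan-Meier estimate then tends to (G − w·g)/(1 − w).

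- g = 0, G = 20%: 0.20/0.95 = 21.1% and 0.20/0.90 = 22.2% for w = 5% and 10%.
- g = 0, G = 35%: 0.35/0.95 = 36.8% and 0.35/0.90 = 38.9%.
- Withdrawn patients half as likely to be event-free as the rest: G/(1 − w/2), so 20% reads 20.5% and 21.1%.
- Withdrawn patients like the rest: no bias.

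Section 10.3.1 plans a one-sided 5% z-test but does not state the variance, so I assume the Greenwood (Wald) form. With 55 complete outcomes it rejects at 17 or more successes: 17/55 gives z = 1.75, and 16/55 gives z = 1.48. The rejection probability at 20% is 3.7%. With g = 0 and each patient withdrawn early with probability w, averaging over the number left gives 5.2% (w = 5%) and 7.8% (w = 10%).

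Timing matters. In a simulation with n = 55 and exponential GRFS, 5% or 10% of patients due an event were censored just before it (about 2 or 4 patients). A true 20% read 21.6% or 23.3%, and rejection was 6.2% or 10.6%, against 3.8% with no withdrawal.

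**5. OS (assumed rates).** Take constant hazards over 12 months. R and M are the 12-month incidences of relapse and NRM, d is the probability of death within a year of relapse, and f is the fraction of relapsers removed at relapse.

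- λ = −ln(1 − R − M), a = λR/(R + M), b = λM/(R + M), m = −ln(1 − d), with time t in years.
- Alive after relapse: A(t) = a(e^(−mt) − e^(−λt))/(λ − m).
- True OS = e^(−λ) + A(1).
- The Kaplan-Meier limit is exp(−∫h), with h(t) = [b·e^(−λt) + (1 − f)·m·A(t)]/[e^(−λt) + (1 − f)·A(t)].

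For R = 15%, M = 10%, d = 50%: λ = 0.288, a = 0.173, b = 0.115, m = 0.693. True OS = 0.750 + 0.106 = 85.6%. With f = 1 the limit is e^(−0.115) = 89.1%.

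| R, M, d | True OS | Overstated, f = 10% | f = 25% | f = 100% |
|---|---|---|---|---|
| 15%, 10%, 50% | 85.6% | 0.3 | 0.8 | 3.5 |
| 25%, 15%, 75% | 72.8% | 0.8 | 2.1 | 9.8 |
| 30%, 15%, 75% | 70.2% | 0.9 | 2.4 | 11.8 |

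Overstatement is in percentage points. The most adverse mix within these ranges (30%, 10%, 75%) gives 1.0, 2.6 and 12.7.

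**The case against.** The strongest reply is that the plan's intent is clear and the clause is discretionary. Removal is tied to the subject's best interests, and the listed reasons are examples. Section 6.6 is categorical about following dosed patients. Section 2.5 counts death from any cause for OS and does not treat relapse as competing for GVHD, which makes sense only if patients are followed past relapse. In 4.1 the words on refusing all follow-up qualify consent withdrawal; extending them to PI removal is an inference. GVHD and disease assessments are marked standard of care in the study calendar, so the clinical data will often exist. OS and GVHD are secondary endpoints, estimated without a test.

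Much of this stands, and it rules out several stronger readings that a reader might infer:

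- That every relapsing patient will be removed. The text does not require this, so an OS overstatement of 3 to 12 points is the extreme case, not the expected one.
- That removal for progression biases the primary endpoint. Relapse is itself a GRFS event, so once recorded it is counted.
- That false rejection goes from about 7% to about 13%. Those figures come from a null-variance rule of 16 or more successes in 55 complete outcomes (6.9% at 20%, 13.5% at 22%). Complete outcomes cannot coexist with 5-10% withdrawn, and the 7% baseline arises from discreteness and the variance chosen, not from withdrawal.

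The reply does not remove the conflict. The withdrawal paragraph refers to removal from the study, gives no route to continued outcome follow-up, and no analysis rule compensates.

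**Conclusion.** The contradiction is certain on the text. The bias is possible and its size unknown, because it depends on how often investigators use the clause. What can be said is that data could be lost, not that they will be.

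If patients are withdrawn for toxicity or illness before any event, and do worse than the rest, the bias in GRFS, OS and NRM favours the drug. Under the early-withdrawal assumptions (5-10% withdrawn, none of whom would have been event-free), a true GRFS of 20% reads 21-22% and one-sided rejection moves from about 4% to 5-8%. These figures shrink to nothing if withdrawn patients resemble the others, and grow if censoring falls just before the event. OS is overstated by about 0.3 to 2.4 points in the three scenarios with 10-25% of relapsers removed. For GVHD after relapse, the documents do not allow a direction to be stated.

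This should be fixed. It is not a flaw that invalidates the design, since the plan's default is follow-up.

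**What to change.** Reconcile 4.1, 4.6 and 6.6.

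- **4.6, Investigator-initiated Withdrawal:** state that a dosed patient withdrawn by the investigator, who has not fully withdrawn consent, stays in follow-up for GVHD, relapse and survival to 12 months after transplant.
- **4.1, Withdrawn status:** limit removal by the local PI to patients removed before the first dose. Do not delete the category: the eligibility text provides for patients who become ineligible before the first dose to be removed and replaced, and they need a status.
- Leave the treatment-stopping criteria as they are. The change concerns data collection only. In particular, do not recast the withdrawal reasons as reasons to end treatment, because they lack the qualifiers in the treatment list.
- Leave the subject's right to full consent withdrawal unchanged. The reasons in the withdrawal paragraph include a subject's own request, so the exception must be explicit.

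The cost is a wording amendment to two paragraphs and slightly more data entry. Most of the assessments are already standard of care. It is best done before further patients are removed, since outcomes not collected at the time may not be recoverable.

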4.7 Lost to Follow-up

The following actions must be taken if a participant fails to return to the clinic for a required study visit and/or is unable to be reached for follow-up:

- The investigator or designee must make every effort to regain contact and/or reschedule a missed visit with the participant.
- A participant is deemed lost to follow-up if his/her status cannot be obtained after all of the following occurs at two consecutive scheduled protocol calendar timepoints:
 - o Three telephone calls (at least one day apart) from the study team are unanswered. AND
 - A letter to the participant's last known mailing address goes unanswered.
 - These contact attempts must be documented in the participant's medical record or study file.
- Update OnCore® (follow-up tab and eCRF) when a participant is officially considered lost to follow-up.
- If a subject is considered lost to follow-up, but subsequently contacts the study team, the subject should be considered in follow-up again.

4.8 Accrual Suspension and Closure

The MCW PI facilitates the suspension and closing of accrual in the following manner:

- OnCore[®] tracks accrual throughout the study.
- If the study must be suspended, OnCore® is updated to a 'suspended' status.
- When the accrual number is reached. OnCore[®] notifies staff of study closure.

4.9 Study Discontinuation and Closure

This study may be temporarily suspended or prematurely terminated if there is sufficient reasonable cause (as determined by the MCW Study PI, DSMC, sponsor, and/or IRB). Written notification, documenting the reason for study suspension or termination, will be provided by the suspending or terminating party to study participants, investigator, funding agency, the Investigational New Drug (IND) sponsor and regulatory authorities. If the study is prematurely terminated or suspended, the MCW Principal Investigator (PI) will promptly inform the MCW Institutional Review Board (IRB), and sponsor and will provide the reason(s) for the termination or suspension. Study participants will be contacted, as applicable, and be informed of changes.

5 STUDY ENTRY AND WITHDRAWAL; STUDY PROCEDURES

5.1 Required Preregistration Screening Tests and Procedures

The study-specific assessments are detailed in this section and outlined in the Study Calendar.

A written, signed informed consent form (ICF) must be obtained before any study-specific assessments are initiated. A signed ICF copy will be given to the subject and a copy will be filed in the medical record. The original will be kept on file with the study records.

MCW Protocol No: PRO00035737 33 Version No. 7 All patients who are consented will be registered in OnCore[®], the MCW Cancer Center Clinical Trial Management System. The system is password protected and meets HIPAA requirements.

5.2 Registration Process

Patients will be approached for this study after the decision to proceed with transplant is made and a suitable HLA-matched donor is identified. Transplant physicians will evaluate the patient eligibility into this study. All source documents that support eligibility include a signed informed consent/HIPAA and signed eligibility checklist. These must be available for review and verification.

At the point of registration, the study staff will register the patient in the electronic database (where applicable), including demographic, consent and on-study information. The patient will be assigned a unique sequence number for the study.

Patients will be enrolled on this trial within 30 days preceding the conditioning regimen for alloHCT.

